OBJECTIVES	
Primary Objectives
 
Phase 1b: The primary objective of this study component is to determine the maximum tolerated dose (MTD) of PAC-1 in combination with entrectinib in subjects with metastatic uveal melanoma, by evaluation of toxicity and tolerability.
 
Phase 2: The primary objective of this study component is to measure 3 months progression-free survival (PFS) rate, using RECIST v1.1, in subjects with metastatic uveal melanoma treated with entrectinib and PAC-1.
 
Secondary Objectives
 
Phase 1b: Evaluate the safety of entrectinib and PAC-1 combination, assessed by the incidence and severity of drug-related adverse events (AE), in subjects with metastatic uveal melanoma.
 
Phase 2
 
 • Evaluate the safety of entrectinib and PAC-1 combination, assessed by the incidence and severity of drug-related AEs, in subjects with metastatic uveal melanoma. • Estimate the ORR in subjects with metastatic uveal melanoma treated with entrectinib and PAC-1. • Estimate DoR in subjects with metastatic uveal melanoma. • Estimate OS rate in subjects with metastatic uveal melanoma treated with entrectinib and PAC-1. 
Correlative/Exploratory Objectives
 
 • Determine pharmacokinetics/pharmacodynamics of PAC-1 alone after single dosing and after repeated dosing and in combination with entrectinib (Phase 1b only). • Determine pharmacokinetics/pharmacodynamics of entrectinib alone after single dosing and after repeated dosing and in combination with PAC-1 (Phase 1b only). • Compare procaspase 3 expression in tumor tissue to degree of clinical response. • Determine correlation between CTC number and clinical response.

STUDY DESIGN	
Single arm study with dose escalation Phase Ib cohort followed by a Phase II cohort. PAC-1 (PO) will be given daily on Days 1 through 21 of each cycle (28-day cycle). Entrectinib (PO) will be given daily on Days 1 through 28 of each cycle. Response will be evaluated after every 2 cycles. Treatment will continue until disease progression based on RECIST criteria or intolerable toxicity.

ELIGIBILITY CRITERIA (See Section 3 for complete list of eligibility criteria)	
Inclusion Criteria
 
 1. Histologically or cytologically confirmed metastatic uveal melanoma. 2. One or more lesions that could be accurately measured using Response Evaluation Criteria in Solid Tumors (RECIST) 1.1. 3. Eastern Cooperative Oncology Group (ECOG) performance status of 0 to 1. 4. Adequate organ function within 14 days of registration. 5. Subjects must have archival tissue (metastatic disease preferred) available or agree to undergo a biopsy prior to C1D1 treatment. 6. Prior therapy is allowed but must have been completed 21 days prior to initiation of protocol therapy and all toxicities must be < Grade 2. 7. Palliative radiation must have been completed 2 weeks prior to the initiation of study therapy. 8. Patient with known brain metastases must have been treated at least 2 weeks prior to enrollment, be asymptomatic from brain metastases, stable on brain imaging, and not be receiving a supra-physiologic dose of steroids (>10 mg prednisone daily or equivalent). 9. All females of childbearing potential must have a urine HCG test or blood HCG test within 2 weeks prior to registration to rule out pregnancy. 
Exclusion Criteria
 
 1. Peripheral sensory neuropathy Grade \geq 2 (per CTCAE v5.0). 2. Active gastrointestinal disease (e.g., Crohn's disease, ulcerative colitis, or short gut syndrome) or other malabsorption syndromes that would reasonably impact drug absorption. 3. Has known history of Human Immunodeficiency Virus (HIV) (HIV 1/2 antibodies). 4. Has known active Hepatitis B or C. Active Hepatitis B is defined as a known positive HBsAg result. Active Hepatitis C is defined by a known positive Hep C Ab result and known quantitative HCV RNA results greater than the lower limits of detection of the assay. For patients with past HBV infection or resolved HBV infection (defined as the presence of hepatitis B core antibody [HBcAb] and absence of HBsAg), the patient is only eligible if they are negative for HBV DNA. 5. Known interstitial lung disease, interstitial fibrosis, or history of tyrosine kinase inhibitor-induced pneumonitis. NOTE: Radiation-induced lung disorders are not included in this exclusion criterion.

	
6. History of retinal pigmented epithelial detachment, central serous retinopathy, or retinal vein occlusion in the unaffected eye; or intraocular pressure 21 mmHg or uncontrolled glaucoma (irrespective of intraocular pressure) in the unaffected eye7. History of uncontrolled seizures8. History of ataxia9. Allergies and adverse drug reaction: History of allergy to study drug components10. Thromboembolic events requiring therapeutic anticoagulation. Concomitant anticoagulation with oral anticoagulants (warfarin, direct thrombin or factor Xa inhibitors), platelet inhibitors (eg. Clopidogrel, high dose aspirin) is prohibited. Low-dose aspirin (\leq100 mg/day), low-dose warfarin (\leq1 mg/day) and prophylactic low molecular weight heparin (LMWH) or similar agents are permitted.11. History of recent (within the past 3 months) symptomatic congestive heart failure or ejection fraction \leq50% observed during screening for the study.12. History of prolonged QTc interval (e.g., repeated demonstration of a QTc interval $>$ 450 milliseconds from ECGs performed at least 24 hours apart).13. History of additional risk factors for torsades de pointes (e.g., family history of long QT syndrome).14. Cardiovascular disorders including unstable angina pectoris, clinically-significant cardiac arrhythmias, myocardial infarction or stroke (including transient ischemic attack [TIA], or other ischemic event) within 6 months prior to registration.15. Active infection requiring intravenous systemic treatment.16. Serious non-healing wound/ulcer/bone fracture within 28 days prior to registration.17. Known uncontrolled, symptomatic brain metastasis or cranial epidural disease.18. Known additional malignancies which require systemic treatment.19. Inability to swallow intact tablets.
--	---

STATISTICAL CONSIDERATIONS	
Phase 2 The primary endpoint of the study is 3 month progression-free survival (PFS) rate, using RECIST v1.1, in subjects with metastatic uveal melanoma treated with entrectinib and PAC-1. Kaplan Meier curve will be used to evaluate PFS, and OS; descriptive statistics for response rate, DoR, and toxicity.
 
Sample Size Previous studies in the target population identified PFS at 3 months of 38%.⁶ We hypothesize PFS at 3 months of 65%. Controlling for a probability of Type I error at 0.05 (one-sided), our sample size in Phase 2 is estimated to be 32 to ensure 90% statistical power in successfully detecting an alternative progression free survival rate at 3 months of 0.65, compared to a null rate of 0.38. With 3 additional patients to account for a 10% drop off rate, sample size for phase 2 study will be 35. Sample size analyses were conducted using the PASS software (NCSS, Kaysville, Utah, USA). With Phase 1b study component, the study will need to have 3 subjects from Dose Level 1 of Phase 1b + 6 subjects from Dose Level 2 of Phase 1b (and carried over to Phase 2 study).

TOTAL NUMBER OF SUBJECTS	Total number of subjects for the study is 38
ESTIMATED ENROLLMENT PERIOD	Estimated 18 months
ESTIMATED STUDY DURATION	Estimated 24 months

[figure not shown]
TABLE OF CONTENTS

ABBREVIATIONS	10
1. BACKGROUND AND RATIONALE.....	12
2 STUDY OBJECTIVES AND ENDPOINTS.....	13
3 ELIGIBILITY REQUIREMENTS	15
4 SUBJECT REGISTRATION	18
5 OVERALL DESIGN AND TREATMENT PLAN.....	18
6 DOSE DELAYS/DOSE MODIFICATIONS	24
7 STUDY CALENDAR & EVALUATIONS	28
8. CORRELATIVE STUDIES AND PROCEDURES.....	31
9. CRITERIA FOR DISEASE EVALUATION	33
11. ADVERSE EVENTS.....	39
12 STATISTICAL CONSIDERATIONS.....	45
13 TRIAL MANAGEMENT	49
14 DATA HANDLING AND RECORD KEEPING	51
15 ETHICS.....	52
16 REFERENCES	53
APPENDIX 1: ECOG PERFORMANCE STATUS	55
APPENDIX 2: DRUG INTERACTIONS WITH ENTRECTINIB.....	56

PHASE 1b SCHEMA

The primary objective of the Phase Ib study is to establish the maximum tolerated dose (MTD) of PAC-1 in combination with entrectinib for subjects with metastatic uveal melanoma, by evaluation of toxicity and tolerability.

Phase 1b

[figure not shown]
Dose Level*	PAC-1 Dose (mg, orally)	Entrectinib (mg, orally)	# of Subjects [#]
-1	625 daily	400 daily	3-6
1	625 daily	600 daily	3-6
2	750 daily	600 daily	3-6

*MTD cohort will be initially expanded to 6 patients, and if no DLT, to Phase 2 study.

PHASE 2 SCHEMA

The primary objective of the Phase 2 Study is to estimate 3 month progression-free survival (PFS) using RECIST v1.1 in subjects with metastatic uveal melanoma.

Phase II

Entrectinib dosed at 600 mg once daily; PAC-1 dosed once daily at RP2D from Phase 1b study.

ABBREVIATIONS

Abbreviation	Definition
AE	adverse event
ANC	absolute neutrophil count
ALK	anaplastic lymphoma kinase
ALT	alanine aminotransferase
ASCO	American Society of Clinical Oncology
AST	aspartate aminotransferase
BUN	blood urea nitrogen
CBC	complete blood count
cm	centimeter
CMP	comprehensive metabolic panel
CNS	central nervous system
CR	complete response
CT	computed tomography
CTCAE	(NCI) Common Terminology Criteria for Adverse Events
CTEP	Cancer Therapy Evaluation Program
CYP	cytochrome P450
dL	deciliter
DOOR	duration of response
ECG	electrocardiogram
ECOG	Eastern Cooperative Oncology Group
ERK	extracellular signal-regulated kinase
FDA	Food and Drug Administration
FDAAA	Food and Drug Administration Amendments Act
FDAMA	Food and Drug Administration Modernization Act
GFR	glomerular filtration rate
h	hour
Hgb	hemoglobin
IB	Investigator's Brochure
IND	Investigational New Drug
IRB	institutional review board
kg	kilogram
lbs	pounds
LDH	lactic dehydrogenase
mg	milligram
min	minute
mL	milliliter
mm ³	cubic millimeters

MRI	magnetic resonance imaging
MTD	maximum tolerated dose
NSCLC	non-small cell lung cancer
NTRK	neurotrophic tyrosine kinase
ORR	overall response rate
OS	overall survival
PAC-1	first procaspase-activating compound
PFS	progression-free survival
PK	pharmacokinetics
PR	partial response
PT	prothrombin time
PTT	partial thromboplastin time
RECIST	Response Evaluation Criteria in Solid Tumor
ROS1	ROS proto-oncogene 1
SAE	serious adverse event
SDEA	Safety Data Exchange Agreement
TKI	tyrosine kinase inhibitor
Trk	tropomyosin-related kinase
ULN	upper limit of normal
US	United States
WHO	World Health Organization
WOCP	women of childbearing potential
wt	weight

1. BACKGROUND AND RATIONALE

1.1 Uveal Melanoma

Uveal melanoma arises from the uveal tract of the eye, which includes the choroid, ciliary body, and iris, and is the most common primary intraocular malignancy in adults.¹ Uveal melanoma is biologically different from cutaneous melanoma² and accounts for approximately 3% to 5% of all melanoma. There are currently no approved or effective systemic treatment options for individuals with metastatic uveal melanoma. Mutations in GNAQ or GNA11 are found in more than 80% of uveal melanomas, resulting in constitutive activation of the RAS/RAF/MEK/ERK pathway.³⁻⁵

1.2 Current Treatment of Uveal Melanoma

There are more than 40 clinical trials reported in uveal melanoma with average response rate of 4%. Current standard of care is dacarbazine. In a recent randomized clinical SUMMIT trial of selumetinib in combination with dacarbazine in patients with metastatic uveal melanoma the objective response rate (ORR) was 3%, with progression-free survival (PFS) of 2.8 months in selumetinib plus dacarbazine treatment group. Three- and 6-month PFS rates were 38% and 10%, respectively.⁶ Overall survival (OS) was only 10 months.

1.3 Entrectinib

Entrectinib is a potent tyrosine kinase inhibitor (TKI) that targets the product of oncogenic rearrangements in neurotrophic tyrosine kinase (NTRK), ROS proto-oncogene 1 (ROS1), and anaplastic lymphoma kinase (ALK). Two phase I trials demonstrated activity in TKI-naïve patients along with substantial intracranial activity. In ROS1-rearranged lung cancers, entrectinib resulted in durable disease control and prolonged PFS. The drug was well tolerated and has a safety profile that includes adverse events mediated by on-target tropomyosin-related kinase (Trk) A/B/C inhibition. Refer to the current investigator's brochure for details regarding adverse events related to entrectinib.

1.4 First Procaspsase-Activating Compound

Members of the caspase family of cysteine proteases are key players in both the initiation and execution of apoptosis.⁸ Most critical to apoptosis is the proteolytic conversion of procaspsase-3 to caspase-3. As both the intrinsic and extrinsic apoptotic pathways converge to activate procaspsase-3, and as caspase-3 has over 100 cellular substrates, the activation of procaspsase-3 to caspase-3 is a pivotal and committed event in the apoptotic cascade.⁹ Procaspsase-3 levels are elevated in a variety of tumors including glioblastoma¹⁰, breast cancer¹¹, colon cancer¹², lung cancer¹³, lymphoma¹⁴, neuroblastoma¹⁵, melanoma¹⁶, and liver cancer¹⁷. First procaspsase-activating compound (PAC-1) is a small molecule, which enhances procaspsase-3 activity *in vitro*¹⁸, induces apoptotic death of cancer cells in culture^{9,18,19}, and has efficacy in multiple mouse xenograft models^{18,20}. There is a strong correlation between cellular procaspsase-3 levels and the apoptosis-inducing properties of PAC-1.¹⁸ PAC-1 has shown toxicity in mice, rats and dogs. The toxicity is more typically observed with high doses. However, in one study testing relatively lower doses of PAC-1 given orally daily for 28 days in dogs, there was evidence of minimal-mild neurodegeneration (unpublished study). Overall, PAC-1 has several attributes which makes this a potentially efficacious anticancer drug in humans. Accordingly, we are presently conducting a study consisting of two components: to determine the maximum tolerated

dose (MTD) of PAC-1 in solid tumor or hematologic malignancy (NCT02355535), and to determine the maximum tolerated dose of PAC-1 when combined with the front-line chemotherapeutic agent, temozolomide, in patients with primary brain tumors (NCT03332355). Primary endpoints are evaluation of tolerability and toxicity. Neurological symptoms of CNS toxicity are being assessed throughout the trial.

PAC-1 has been dosed in 44 human patients through 7 dose levels of PAC-1 (range: 75-750 mg). Two patients progressed during the first cycle of PAC-1 therapy. Thirty-two patients received PAC-1 for at least 2 dosing cycles (a cycle is 21 days of daily dosing followed by 7 days of no drug). As a result of stable disease responses, six patients received PAC-1 for 4 cycles, three patients received PAC-1 for 6 cycles and two patients received PAC-1 for 10 cycles. No serious adverse events (SAEs) associated with PAC-1 administration have been observed. Further, after careful review of all neurological and neurocognitive assessments and data collected through dose level 7 (750 mg) there were no signs of neurotoxicity associated with PAC-1 dosing. In this study, physicians will utilize the MOCA-Montreal Cognitive Assessment Test Form for subject assessment at screening and Day 1 of each Cycle.

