6.2 Dose Modifications for PAC-1 Toxicity

CTCAE v 5 Adverse Effects Terms & Descriptions)	PAC-1 Dose Modifications
Any other grade 3 non-hematologic toxicity	Hold dose until improvement to grade ≤ 1 then decrease dose by one dose level below level that caused toxicity.
Grade ≥ 2 neurologic toxicity detected at any time while on study treatment	Hold dose until improvement to grade ≤ 1 then decrease dose by one dose level below level that caused toxicity.
Any grade cerebrovascular ischemia or hemorrhage	Discontinue treatment.
Any other grade 4 non-hematologic toxicity	Discontinue treatment.
Neutrophils < 500 cells/mm 3	Hold dose until improvement to grade ≤ 1 then decrease dose by one dose level below level that caused toxicity.
Febrile Neutropenia	Hold dose until improvement to grade ≤ 1 then decrease dose by one dose level below level that caused toxicity.
Platelets $< 25,000/\text{mm}^3$ or platelets $< 50,000/\text{mm}^3$ with bleeding	Hold dose until improvement to grade ≤ 1 then decrease dose by one dose level below level that caused toxicity.
Any other grade 3 hematologic toxicity	Hold dose until improvement to grade ≤ 1 then decrease dose by one dose level below level that caused toxicity.
Any other grade 4 hematologic toxicity	Discontinue treatment.

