10.1.7 Warnings and Precautions

Observation and assessment of hematological and non-hematological markers of toxicity in research dogs raised a possibility that PAC-1 may cause neurodegenerative changes in the brain, and therefore neurological and neurocognitive examinations was performed in NCT02355535 study. No neurologic nor neurocognitive changes were seen in this study, therefore these evaluations will not be performed in this study.

In NCT02355535 (Procaspsase Activating Compound-1 (PAC-1) in the Treatment of Advanced Malignancies - Component 1), one Component 1 patient who was in the 625mg/day cohort experienced an intracranial hemorrhage related to brain metastases where a possible attribution to PAC-1 could not be ruled out. In order to monitor and ensure patient safety, patients should have a baseline brain MRI for future comparison if needed. Coagulation tests will be done prior to dosing on Day 1 of each treatment cycle.

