11.1.3.2 The PAC-1 Events of Special Interest are

- Grade ≥ 3 Neurologic disturbances
- Grade ≥ 3 Cognitive disturbances

11.1.3.3 Non drug specific adverse events of special interest for this study include the following

- Cases of potential drug-induced liver injury that include an elevated ALT or AST in combination with either an elevated bilirubin or clinical jaundice, as defined by Hy's law:
 - Treatment-emergent ALT or AST $> 3 \times$ ULN in combination with total bilirubin $> 2 \times$ ULN
 - Treatment-emergent ALT or AST $> 3 \times$ ULN in combination with clinical jaundice
- Suspected transmission of an infectious agent by the study drug, as defined below:
 - Any organism, virus, or infectious particle (e.g., prion protein transmitting transmissible spongiform encephalopathy), pathogenic or non-pathogenic, is considered an infectious agent. A transmission of an infectious agent may be suspected from clinical symptoms or laboratory findings that indicate an infection in a patient exposed to a medicinal product. This term applies only when a contamination of the study drug is suspected

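### Section 1.4 reports no PAC-1-associated SAEs while Section 10.1.7 reports a possibly attributable intracranial hemorrhage, and lower-grade, non-serious cerebrovascular events have no expedited report

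*Combined protocol and SAP*

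**What the plan says.** **Earlier experience.** Section 1.4 covers 44 patients treated at seven dose levels from 75 to 750 mg and concludes: "No serious adverse events (SAEs) associated with PAC-1 administration have been observed".

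**The hemorrhage.** Section 10.1.7 reports on a patient treated at 625 mg/day in Component 1 of NCT02355535, who "experienced an intracranial hemorrhage related to brain metastases where a possible attribution to PAC-1 could not be ruled out".

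**This trial's dose.** The dose-level table in Section 5.1 marks dose level 1, with PAC-1 at 625 mg daily, as the starting level.

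**How the protocol treats such events.** Section 5.1.2 counts cerebrovascular ischemia or hemorrhage as a DLT at any grade or duration if it is at least possibly related and falls in Cycle 1. The PAC-1 modification table in Section 6.2 has a row for "Any grade cerebrovascular ischemia or hemorrhage", with discontinuation as the listed action.

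**What is reported fast.** Section 11.3.2 requires SAEs and events of special interest (AESIs) to be reported within 1 business day. The PAC-1 list in Section 11.1.3.2 has two entries: "Grade ≥ 3 Neurologic disturbances" and "Grade ≥ 3 Cognitive disturbances".

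**The concern.** Two things do not fit together.

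The first is the background safety statement. IRBs, investigators and the DSMB may take Section 1.4 as the summary of human safety for PAC-1. It gives a clean record across a dose range that includes 625 mg, while a later section of the same document describes an intracranial hemorrhage at that dose with PAC-1 not excluded as a cause. The trial also admits patients with treated, stable brain metastases (Section 3.1, item 10), so the context of that case is relevant here.

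The second is the reporting rule. The protocol treats cerebrovascular events as important at any grade when it defines DLTs and PAC-1 modifications. Its PAC-1 special-interest list starts at Grade 3 and does not name them. A low-grade event could therefore meet the Section 6.2 row without the coordinating organization, the sponsor-investigator or the two companies hearing of it within 1 business day. The DSMB meets only twice a year unless an extra meeting is called (Section 13.1).

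**Working it through.** **Step 1. Do Sections 1.4 and 10.1.7 conflict?**

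- *Same exposure.* Section 1.4 spans seven levels up to 750 mg. Section 10.1.6 describes Component 1 of NCT02355535 as running through dose level 7 at 750 mg. The 625 mg/day cohort lies inside that range. No data cut-off is given in either section.
- *Relatedness.* Section 10.1.7 leaves a possible attribution open. In this protocol, possible means that the event may be related (11.2.4), and DLTs are counted from that threshold upward (5.1.2).
- *Seriousness.* Section 10.1.7 gives neither grade nor outcome and does not call the event an SAE. Under Section 11.1.2 an intracranial hemorrhage would very probably qualify as life-threatening, as leading to hospitalization or as medically significant, but that is an inference.

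The two sections are inconsistent unless a cut-off or a narrower meaning of associated explains the difference. Neither is stated.

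**Step 2. How large is the difference?** The plan gives no rate to reproduce. Assume that the patient is one of the 44 and use exact (Clopper-Pearson) two-sided 95% limits.

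- 0/44: upper limit = 1 - 0.025^(1/44) = 0.080, or 8.0%.
- 1/44 = 0.0227, or 2.3%. Lower limit = 1 - 0.975^(1/44) = 0.0006, or 0.06%. Upper limit = 97.5th percentile of Beta(2, 43) = 0.120, or 12.0%.

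The number treated at 625 mg/day is not given, so no rate at that dose can be computed. With assumed cohorts of 3, 6 or 12 patients, one event would be 33%, 17% or 8%. The intervals for 0/44 and 1/44 overlap heavily. What changes is the statement of none, more than any estimate of risk.

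**Step 3. Which cerebrovascular events get a 1-business-day report?**

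| Event | Phase 1b, Cycle 1 | Later cycles, and Phase 2 |
|---|---|---|
| Judged serious, or Grade 4-5 | SAE route (11.1.2, 11.2.5 note d, 11.3.2) | Same |
| Grade 3, not judged serious | AESI if read as a neurologic disturbance; DLT if at least possibly related | AESI on the same reading |
| Grade 1-2, not judged serious | DLT if at least possibly related; no 1-day report | eCRF entry as an AE (11.3.1); no 1-day report |

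The other two lists do not close the last row. The entrectinib list (11.1.3.1) would catch a low-grade event only if it showed itself as syncope or as a Grade 2 or higher cognitive disturbance. The non-drug-specific list (11.1.3.3) concerns liver injury and infection.

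In Phase 1b Cycle 1, the DLT count would bring the event to light, because the next cohort waits on it. After Cycle 1 that safeguard ends. It also does not apply to the 29 subjects enrolled directly into Phase 2 (35 - 6 = 29, Section 12.3.1), because the DLT rules belong to the Phase 1b plan.

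**The case against.** The best defense has four parts.

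- *The bleed had another cause.* Section 10.1.7 describes it as related to brain metastases, and the attribution to PAC-1 is only that it could not be excluded. It comes from another trial, whose relatedness scale is not in view. This stands as a reason not to call Section 1.4 false. It does not remove the inconsistency, because the possible attribution is the document's own statement.
- *The risk is disclosed.* It appears under Warnings and Precautions. Eligibility requires brain metastases to be treated, asymptomatic and stable, and excludes patients with thromboembolic events requiring therapeutic anticoagulation. This also stands: nothing is hidden, but one document gives two different accounts.
- *Serious bleeds are already covered.* This is correct. A reader might infer that the expedited channel would miss a recurrence of the Section 10.1.7 case. The documents do not support that. A serious hemorrhage, related or not, goes to the coordinating organization within 1 business day and on to both companies within 1 more (11.3.2.1, 11.3.2.2). A Grade 3 event can also be read as a neurologic disturbance. Only the Grade 1-2, non-serious event is left.
- *That remainder is small.* It is, and such an event is still recorded as an AE. But the protocol itself chose any grade as the threshold in Sections 5.1.2 and 6.2, and gives no reason for a higher one in reporting.

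**Conclusion.** The point holds in a limited form. Sections 1.4 and 10.1.7 are inconsistent and must be reconciled. The PAC-1 special-interest list is narrower than the DLT and modification rules for the same event, which leaves Grade 1-2, non-serious cerebrovascular events without a 1-business-day report. No endpoint, sample size or analysis is affected. The Section 1.4 wording alone would be a background correction. The reporting gap is what makes the point worth acting on.

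The figures (2.3% against 0%, with upper limits of 12.0% and 8.0%) assume that the patient is among the 44, and they pool all doses.

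Two further inferences should be resisted. A reader might project the 1/44 rate onto the 38 planned subjects. Over the exact interval, the chance of at least one event, 1 - (1 - p)^38, runs from about 2% at p = 0.0006 to about 99% at p = 0.12, so the projection says nothing useful. A reader might also infer that the consent form misstates the risk. The consent pages are not in view, so that cannot be judged.

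**What to change.** 1. Reconcile Section 1.4 with Section 10.1.7. State the 625 mg/day case with both its brain-metastasis context and the possible attribution to PAC-1, and give the event's grade, its seriousness and the data cut-off for the 44 patients. If the event was not serious, or came after the cut-off, say so.
2. Bring Section 10.1.6 into line. It calls the human risks of oral PAC-1 unknown and reports no neurologic changes through 750 mg, without mentioning the case.
3. Add cerebrovascular ischemia or hemorrhage of any grade to the PAC-1 list in Section 11.1.3.2, so that reporting uses the same threshold as Sections 5.1.2 and 6.2.

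The cost is a text correction, one line in a list and a few extra expedited reports. No visit, test or analysis is added.
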